## 4.2 BRAIN IMAGING PROTOCOLS

### 4.2.1 MRI and MRS Protocols

Subjects will be asked to lie supine in the ultra-high resolution 7T multimodal MRI scanner at The Imaging Centre of Excellence, based in a comprehensive clinical setting in Glasgow. Using a MAGNETOM Terra 7T scanner (Siemens Healthcare, Erlangen, Germany) and a single channel transmit, 32 channel receive radiofrequency head coil (Nova Medical, Wilmington, MA), we will obtain neurobiological surrogate measures of functional connectivity and glutamate:

**1) Functional connectivity** - a resting state BOLD-fMRI scan will be undertaken. Functional connectivity MRI (fcMRI) investigations are conducted with subjects resting in the scanner. Ten minutes of whole-brain resting state fMRI data will be collected using a simultaneous-multi-slice (SMS) echoplanar-imaging (EPI) sequence of factor=3. A whole-brain T1-weighted structural image will also be collected using a twice magnetization-prepared rapid gradient echo (MP2RAGE) sequence. During the resting state, subjects will be instructed not to undertake any particular task and to stay awake with their eyes open on a fixation cross. Whole brain coverage will be performed. Data will be pre-processed and analysed using software such as statistical parametric mapping (SPM) version 12 (SPM12, Wellcome Department of Cognitive Neurology, London, United Kingdom) and the Conn (Cognitive and affective neuroscience laboratory, MIT, Cambridge, USA) functional connectivity toolbox, all running on MATLAB 2017a.

Upon collection of resting state fcMRI data, pre-processing steps will include the removal of physiological artefacts, motion correction, realignment, registration, normalization and smoothing. Connectivity indices will be generated from matrices informed by our a priori determined regions of interest (DMN-Insula and DAN-IPL).

**2) Glutamate Imaging** – a magnetic resonance spectroscopy scan will be undertaken in order to detect the glutamate concentration. A single voxel sequence will be employed with semi-LASER preparation. A 20x20 mm^3 voxel will be placed in the R posterior insula and shimming of the static magnetic field will be performed using advanced methods best suited to MRS acquisition at 7T, such as FASTMAP. Spectra will be analysed and quantified in JMRUI or LCModel.

In addition, multi-voxel techniques will be employed to provide quantitative maps of glutamate concentration across the brain. These will include chemical exchange saturation transfer (CEST) in the glutamate-weighted form, or GluCEST, which indirectly measures the glutamate present in tissue by measuring the chemical exchange between the glutamate amine spins and the protons present in the bulk water. GluCEST will be applied in one axial slice and one sagittal slice, chosen from the T1 acquisition. The sequence parameters will be slice thickness of 5 mm, field-of-view of 200 x 200 mm^2, matrix size 192 x 192, TR = 16 s, a saturation pulse train of 10 x 100 ms pulses followed by a FLASH readout with flip angle = 10°, TR/TE = 5.5/2.6 ms.

Should any incidental clinically relevant abnormal MRI scan findings be observed that in the opinion of the Investigator may put the participant at risk, a referral will be made to the appropriate speciality. Any incidental finding review will be managed according to Glasgow Centre for Research Imaging (CRIF) processes and Glasgow Clinical Trials Unit (CTU) SOPs.

#### **4.2.2 Ultrasound Protocol**

Rheumatoid arthritis is characterised by synovitis with symmetrical involvement. An optional ultrasound scan of pre-determined joints and up to 2 symptomatic joints with active disease will be performed at baseline and at the 12-week visit. This will provide a robust surrogate measure of peripheral inflammation.

The wrists, MCPs, PIPs joints of hands, knees, MTPs of both feet, and the 2 most symptomatic joints (if applicable) will be scanned and graded using the EULAR-OMERACT combined score. The ultrasonographic evaluation will further characterise the synovium involvement in the participants and will help to evaluate the response to treatment.

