#### 4.1.2 VISIT 2 : Week 12 ± 14 days

- ACR/EULAR Classification Criteria for RA
- EULAR Disease Activity Score (DAS28)
- CDAI
- SDAI
- 7-Day Symptom Diary (Number Rating Scale)
- American College of Rheumatology Fibromyalgia scale

- McGill Pain Questionnaire
- Michigan Body Map Regional Pain
- PROMIS-Depression
- PROMIS-Anxiety
- PROMIS-Fatigue
- PROMIS-Sleep related impairment
- PROMIS-Physical functioning short form
- PROMIS-Pain inference
- Pain Number Rating Scale
- FACIT Fatigue Scale Global Impression of Change (participant)
- Cognitive failures questionnaire
- Sickness Questionnaire
- 7T MRI protocol
- Ultrasound of joints of interest
- Quantitative sensory testing (QST)
- Blood draw for immunophenotyping
- Drug assessment

Estimated visit time 3.5 hours

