### **4.3.2 Secondary Outcome Measure(s)**

The secondary outcome measures will be:

- Changes in clinical phenotype, pain, depression and anxiety as measured by
  - EULAR Disease Activity Score (DAS28)
  - CDAI
  - SDAI
  - 7-Day Symptom Diary (Number Rating Scale)
  - American College of Rheumatology Fibromyalgia Scale
  - McGill Pain Questionnaire
  - Michigan Body Map Regional Pain
  - PROMIS-Depression
  - PROMIS-Anxiety

- PROMIS-Fatigue
- PROMIS-Sleep related impairment
- PROMIS-Physical functioning short form
- PROMIS-Pain inference
- Pain Number Rating Scale
- FACIT Fatigue Scale
- Global Impression of Change (Participant)Cognitive Failures Questionnaire
- Sickness Questionnaire
- Synovitis score (from joint ultrasound)
- Pain sensitivity variables (from QST measures)

- Changes in inflammatory cytokines/chemokines

from baseline (day 0) to Visit 2 (week 12), following Olumiant treatment in RA.

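### Section 4.2.2 does not fix the extra symptomatic joints across visits, so the change in ultrasound synovitis score may compare different joints

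*Combined protocol and SAP*

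**What the plan says.** Section 4.2.2 describes an optional scan of pre-determined joints plus "up to 2 symptomatic joints with active disease will be performed at baseline and at the 12-week visit". Its second paragraph gives the fixed list as "The wrists, MCPs, PIPs joints of hands, knees, MTPs of both feet" and adds that "the 2 most symptomatic joints (if applicable) will be scanned and graded using the EULAR-OMERACT combined score".

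The same section explains the purpose of the scan: "This will provide a robust surrogate measure of peripheral inflammation". It also says that the evaluation "will help to evaluate the response to treatment", so the comparison between visits matters. Sections 2.2 and 4.3.2 list the change in an ultrasound synovitis score from baseline to week 12 as a secondary outcome. Neither gives a formula.

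The visit lists in sections 4.1.1 and 4.1.2 both say only "Ultrasound of joints of interest". Section 7.3 plans to correlate changes in pain, clinical and immune measures with the MRI regions found significant in the primary analysis.

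**The concern.** A change score is interpretable only if the same thing is measured twice. Here part of the scanned set depends on which joints are symptomatic, and nothing carries the baseline choice forward to week 12. A sonographer following the text could choose again at Visit 2, or scan no extra joint if none is then symptomatic.

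This matters more here than in most trials. The rationale (section 1.1) is that most of the drug's pain benefit is not explained by markers of peripheral inflammation, and the hypothesis (section 1.3) separates a fibromyalgia-type pathway from an inflammatory one. If symptoms decide which joints are graded, pain can enter the measure that is meant to stand for inflammation. The change score could then track an MRI region in the section 7.3 analysis partly because it carries symptom change.

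**Working it through.** The plan gives no ultrasound score, expected change, SD or power, so there is no figure to reproduce. The check is a comparison of the text, followed by an illustration on stated assumptions.

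**1. The text side by side**

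- *Which extra joints?* The opening paragraph of 4.2.2 requires a joint to be symptomatic and to have active disease. The second paragraph takes the two most symptomatic and does not mention active disease. These are different rules.
- *How many?* One paragraph says up to two, the other two if applicable. Both allow the number to differ between visits.
- *Chosen when?* Neither paragraph says. Both visits are named for the scan, and no sentence says that the baseline joints are rescanned.
- *Do they count in the score?* Not stated. They are scanned and graded with the fixed list, and no rule for combining grades is given.

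**2. Size of the joint set** (assumptions: grade 0 to 3 per joint; the plan gives no joint count)

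- Fixed list: 2 wrists + 10 MCP + 8 or 10 PIP-level joints + 2 knees + 10 MTP = 32 or 34 joints.
- Maximum sum: 3 × 32 = 96, or 3 × 34 = 102.
- Two extra joints outside the list add at most 2 × 3 = 6 points. Their share of the maximum is 6/102 = 5.9% or 6/108 = 5.6%.

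**3. Shift for one participant if extra joints are not rescanned** (true synovitis unchanged, sum score, joints outside the fixed list)

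- Shift = −(joints lost) × (grade).
- Two joints lost: −2 at grade 1, −4 at grade 2, −6 at grade 3.
- At grade 2, with assumed fixed-list sums of 10, 20 and 30, the false fall is 4/14 = 29%, 4/24 = 17% and 4/34 = 12%.
- A mean per joint does not remove it. With 34 fixed joints, the mean goes from 14/36 = 0.389 to 10/34 = 0.294 (a 24% fall), from 24/36 = 0.667 to 20/34 = 0.588 (12%), and from 34/36 = 0.944 to 30/34 = 0.882 (7%).

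**4. Group mean shift**

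- If a share q of participants loses both joints at grade g, the mean shift is −2 × g × q.
- At grade 2 it is −1, −2, −3 and −4 points for q = 0.25, 0.5, 0.75 and 1. The documents give no value for q.

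**5. When the shift is zero or reverses**

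- Extra joints already on the fixed list and counted once: 0.
- Same joints rescanned whatever their symptoms: 0.
- Two grade-2 joints replaced by two others: shift = (sum of the two new grades) − 4, which runs from 0 − 4 = −4 to 6 − 4 = +2.
- No extra joint at baseline and two grade-3 joints added at week 12: +6.

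**The case against.** The strongest reply is that the section can be read as describing one set of joints scanned twice, and that both visit lists use the same phrase for it. Re-selection at week 12 is not stated, nor is the inclusion of the extra joints in the score. Section 7.1 also defers statistical detail to a fuller analysis plan, which could restrict the score to the fixed list. All of this is fair, and it is why the point is conditional. It does not dispose of it: the benign reading is not stated either. A later analysis plan can exclude joints from the score, but it cannot recover a baseline joint that was not rescanned.

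A second reply is that the active-disease condition keeps pain out of the choice. It does so only in part. Under that rule a joint must still be symptomatic, so one with persisting synovitis that has stopped hurting could be dropped, and the other paragraph omits the condition.

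A reader might infer that pain relief alone will lower the score. The documents do not support that. It needs re-selection at week 12, extra joints outside a list that already covers wrists, MCPs, PIPs, knees and MTPs, persisting synovitis in the dropped joints, no replacement of similar grade, and a score that includes them. A reader might also infer a false correlation between pain change and synovitis change in section 7.3. That section relates changes to MRI regions, not pain to synovitis. Any false-positive rate or induced correlation would need SDs and joint-loss rates that the plan does not give, so none is claimed.

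**Conclusion.** The gap is real but bounded. Section 4.2.2 leaves open whether the extra joints are the same at both visits, words their selection in two incompatible ways, and leaves the score undefined. The change score may therefore compare different joints or different numbers of joints, and symptoms can affect which ones.

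The illustrative size is 4 points for a participant who loses two grade-2 joints, with a possible range from a false fall of 6 to a false rise of 6. This assumes 0 to 3 grading, a sum score and extra joints outside the fixed list.

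The consequence is confined to one optional measure among about 20 secondary ones and to its correlation with MRI regions. The primary connectivity and glutamate endpoints are untouched. It is worth correcting because ultrasound is the study's stated surrogate for peripheral inflammation and the correction costs little.

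**What to change.** In section 4.2.2:

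- State that the change in synovitis score is calculated on the fixed list only (wrists, MCPs, PIPs, knees, MTPs), with the identical set at both visits, and say how the joint grades are combined.
- State that any extra symptomatic joints are selected once at Visit 1, rescanned at Visit 2 whether or not they are still symptomatic, and reported separately and descriptively. They should stay out of the main score even when rescanned: joints picked as worst at baseline tend to look better later through regression to the mean.
- State that joints newly symptomatic at Visit 2 are recorded but not scored.
- Reconcile the two descriptions of how the extra joints are chosen.

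The cost is a short protocol amendment, with the ethics and R&D approvals that section 12 requires, and a change to the ultrasound worksheet. No more joints are scored than the plan already allows. The trade-off is that extra joints outside the fixed list no longer count in the main score.

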#### **4.2.3 Quantitative Sensory Testing Protocol**

Quantitative Sensory Testing (QST) is a standardised methodology to study pain sensitivity in humans. A QST protocol includes a series of noxious and non-noxious stimuli delivered to a patient, followed by a semi-objective method for the patient to rate their perception of each stimulus. In this study, participants will have the option to complete a fully validated QST battery to characterise pain sensitivity as a sickness behaviour variable. All participants who consent to this procedure will undergo familiarisation training prior to data collection to reduce QST-related anxiety.

Pressure pain sensitivity (15-20 minutes) will be assessed using a digital algometer with a 1 cm^2 rubber probe to quantify pressure pain thresholds (PPT) at multiple body sites. Pressure will be manually increased at a rate of 50 kPa/s (1000 kPa max). Participants will press a response button to indicate their first sensation of pain. Pressure intensity at the time of button press is recorded as the PPT. Measurements will be conducted 3 times per site (with 20s intervals) with means used for analysis.

The multimodal automated sensory testing (MAST) system^18 will be performed. The MAST testing will be not be performed in ineligible patients with recent or habitual use of artificial nails. The MAST system will apply pressure at the thumbnail in a controlled systematic manner to derive a measure of pressure intensity that evokes a moderate level of pain (i.e., Pain = 50/100), as well as PPT and tolerance metrics (note inflamed joints will be avoided). The system delivers an ascending series of discrete pressures (5s duration; 4 kg/cm^2/s ramp rate) at 20s intervals, beginning at 0.25 kg/cm^2 and increasing in 0.25-0.50 kg/cm^2 steps. Pain intensity will be rated verbally after each stimulus on a 0-100 numerical rating scale (NRS). The test will be terminated at a maximum pressure of 10 kg/cm^2 or when subjects reach their tolerance. This ascending test will be followed by a random staircase paradigm. MAST pain ratings will be used to interpolate *Thumb Pain* = 50, defined as the pressure intensity that evokes a moderate level of pain (i.e., 50/100). Other variables that will also be derived include: 1) thumb-PPT, defined as the first

thumb pressure in a series of at least two consecutive thumb pressures that elicited a pain rating > 0, and 2) *Pressure Pain Tolerance (thumb-TOL)*, defined as the highest pressure tolerated.

Cuff algometry (10 minutes) will be used to measure deep muscle tonic pain. This consists of a computer-controlled air compressor which delivers varying degrees of pressure to a Velcro-adjusted cuff applied to one gastrocnemius muscle. We will conduct a brief calibration procedure to find a pressure intensity that evokes moderate pain and then apply that intensity for 6 minutes. Pain and sensory unpleasantness ratings will be obtained every 60s.

Temporal Summation (4 minutes) is an effect where there is an increase in the perceived intensity of pain in response to sequential stimuli of equal physical strength. A 256 or 512 mN pinprick stimulus will be applied once to the dominant forearm, followed by a train of 10 identical stimuli (1 Hz). Following the single stimulus and the train of 10 stimuli, patients will report the pain intensity of the pinprick sensation verbally using a 0-100 NRS. This procedure will be repeated thrice. The mean pain rating of the three stimulus trains will be divided by the mean pain rating of the single stimuli to calculate a wind-up ratio (WUR); a WUR >1 indicates temporal summation.

Aversion to visual stressors (10 minutes) will be used to probe mechanisms of Global Sensory Sensitivity that bypass somatic peripheral receptors and the spinal cord. Specifically, participants will be presented with a flashing blue/yellow checkerboard pattern (see APPENDIX). Participants will be acclimatised to a dark room with their eyes perpendicularly aligned 15-inch away from a 15-inch high-resolution, calibrated LED monitor displaying the visual stimulus. Illuminance will be verified using a calibrated light meter. Each visual stimulus intensity level and the entire task will be rated on both sensory intensity and unpleasantness scales with overall task ratings.

The MAST system is being used as a Research Tool and not for clinical purposes.

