### **3.3 EXCLUSION CRITERIA**

- Inability to provide written informed consent.
- Severe physical impairment (e.g. blindness, deafness, paraplegia).
- Pregnant or breast feeding.
- Contraindications to MRI (e.g. severe claustrophobia).
- Major confounding neurological disease including Multiple Sclerosis, Stroke, Traumatic Brain Injury, Parkinson's Disease, Alzheimer's Disease
- Previous targeted synthetic (e.g. Olumiant, tofacitinib) DMARD exposure.
- Co-morbid medical conditions that may significantly impair physical functional status
- Medical or psychiatric conditions that in the judgment of study personnel would preclude participation in this study (e.g., malignancy, psychosis, suicidal ideation)
- BMI  $>$  40 or unable to lie comfortably in MRI

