#### **Recording and reporting of adverse events**

The study is considered to be of low risk and is primarily an observational study. The MRI scanning procedure is the principal trial specific procedure and safety reporting will be focussed around this procedure

Adverse events and serious adverse events will be collected only during the period of time the participant attends clinic for their MRI scan i.e. from the time the participant begins preparation for the scan until 24 hours post scan.

In addition to Sponsor requirements the investigators have a contractual agreement with the MAH to report any SARs suspected to be related to olumiant within 15 days of investigator awareness. These events should be recorded and reported in line with the manufacturers requirements.

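### The flashing-checkerboard test in the optional QST battery has no screen for epilepsy, seizures or photosensitivity, so protection rests on general exclusion criteria not linked to the test

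*Combined protocol and SAP*

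**What the plan says.** The QST battery is voluntary: "participants will have the option to complete a fully validated QST battery" (section 4.2.3). One component probes aversion to visual stressors. It is timed at 10 minutes, and in it "participants will be presented with a flashing blue/yellow checkerboard pattern". On viewing conditions the section says: "Participants will be acclimatised to a dark room with their eyes perpendicularly aligned 15-inch away from a 15-inch high-resolution, calibrated LED monitor". The stimulus is graded: "Each visual stimulus intensity level and the entire task will be rated on both sensory intensity and unpleasantness scales". The schedule of assessments and sections 4.1.1 and 4.1.2 place QST at both Visit 1 and Visit 2.

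Two exclusions in section 3.3, repeated in the synopsis, could bear on a seizure history. One is "Major confounding neurological disease including Multiple Sclerosis, Stroke, Traumatic Brain Injury, Parkinson's Disease, Alzheimer's Disease". The other is "Medical or psychiatric conditions that in the judgment of study personnel would preclude participation in this study", illustrated by malignancy, psychosis and suicidal ideation.

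Section 4.2.3 does set a restriction for a single component elsewhere in the battery: "The MAST testing will be not be performed in ineligible patients with recent or habitual use of artificial nails". It sets none for the visual task.

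Under section 6.3, adverse events are collected only around the MRI scan, "from the time the participant begins preparation for the scan until 24 hours post scan".

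**The concern.** A flashing, high-contrast-colour pattern shown close up in the dark is the kind of stimulus for which one expects a protocol to say who should not see it. This one does not. Someone with well-controlled epilepsy, or with one past light-triggered seizure, might not be regarded as having a major or a confounding disease. That person could pass every named criterion, agree to the optional QST and be shown the checkerboard without any step in the plan prompting staff to stop and ask.

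What is at stake is participant safety in a procedure that is done only for research, is optional, and contributes one part of one secondary outcome (the pain sensitivity variables in sections 2.2 and 4.3.2). It offers the participant no clinical benefit to set against an avoidable hazard, in a study that section 6.3 describes as low risk.

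**Working it through.** The protocol gives no figure to reproduce. The check is a comparison of its sections.

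1. **Exposure.** The planned sample is 20 participants (synopsis, section 7.6) with two visits (section 4.1). The upper bound is 20 × 2 = 40 sessions of about 10 minutes, reached only if everyone consents to QST and attends both visits. Actual uptake is not predicted.

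2. **Named exclusions.** The synopsis criteria and sections 3.2 and 3.3 contain no mention of epilepsy, seizures or photosensitivity. The MRI contraindication criterion gives only severe claustrophobia as its example.

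3. **General exclusions that might apply.** The neurological criterion lists five conditions after the word *including*, so the list is open, but its qualifiers are *major* and *confounding*. Neither describes sensitivity to a visual stimulus. The judgment clause asks whether a condition precludes taking part in the study. It is all or nothing: it does not provide for a participant who is suitable for the study but not for one optional test.

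4. **Screening steps.** Past medical history is taken at Visit 1 only (schedule of assessments, sections 4.1.1 and 4.1.2). A medically qualified investigator confirms eligibility (section 3.4). The safety screening form in section 6.3 is described for MRI hazards. No step tells staff to connect a seizure history with the visual task, and nothing prompts the question again at Visit 2.

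5. **Comparison within section 4.2.3.** The automated thumb-pressure test (MAST) has a participant restriction (artificial nails), a site precaution (inflamed joints avoided), a pressure ceiling and a stop at tolerance. The hand-held algometer has a maximum of 1000 kPa. For the visual task the section describes a check of illuminance with a light meter, but gives no value, flash rate or contrast, no participant restriction and no stopping rule. Component-level protection is therefore a form the protocol already uses, and this component lacks it.

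6. **Adverse event window.** Collection starts when preparation for the scan begins and ends 24 hours after it. MRI and QST belong to the same visits, but the protocol does not fix their order. An event in QST done after the scan, within 24 hours, is inside the window. An event in QST done before scan preparation is outside it.

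**The case against.** The strongest reply is that such a participant is not left without protection. The neurological list is open, so an investigator may place epilepsy under it. Study personnel may exclude on judgment, a medically qualified investigator confirms eligibility, and a medical history is on file. All of this stands. A reader might infer that the plan makes people with epilepsy eligible for the stimulus, or that no criterion could exclude them. The documents do not support that: exclusion is left to discretion, not ruled out.

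A reader might also infer that the stimulus is known to provoke seizures. The protocol gives no flash frequency, contrast or luminance, the appendix figure is not available, and its caption adds no parameters. *Potentially* seizure-provoking is as far as the text allows.

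The participant information sheet and consent pages are not in the reviewed material, and section 13.2 says that risks are explained in writing and verbally. A warning may sit there. That would help, but it would not be a restriction in the protocol.

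On safety reporting, it is tempting to say that QST events go unreported. That is too strong. Section 6.3 defines relatedness by any research procedure, and because only MRI events are listed as expected, a serious QST-related event within the window would count as unexpected and go to the sponsor within 24 hours. Only the ordering gap in step 6 remains.

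Finally, a reader might argue that a seizure would cost the imaging analysis a participant. That requires a seizure and then loss of the scans, and section 7.6 already allows for three dropouts from 20, leaving 17. The argument adds nothing secure.

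**Conclusion.** The point holds in a limited form. No criterion names epilepsy, seizures or photosensitivity, the visual task has no screen of its own, and the two general exclusions that could protect an at-risk participant are not linked to the test. The judgment clause also offers only removal from the whole study, when leaving out one optional component would do.

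The size is bounded by exposure: at most 40 sessions of about 10 minutes, fewer with incomplete QST uptake. The probability of harm cannot be derived. The documents give neither the frequency of a relevant history among these patients nor the stimulus parameters, and the chance that someone has such a history would in any case not be the chance of a seizure. The conclusion rests on the text comparison and on the assumption that no test-specific screen exists in material outside these documents. No primary endpoint or planned analysis is affected. It is worth acting on because the change is small and the procedure is optional and for research only.

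**What to change.** In section 4.2.3, add a restriction in the same form as the one for MAST: the visual-stressor task is not performed in participants with a history of epilepsy, seizures or photosensitivity. Ask about this history with the past medical history at Visit 1, and again before the test at Visit 2. State that these participants remain in the study and may do the other QST components.

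Two small additions would close the related gaps. Give the flash rate, contrast and luminance of the stimulus, so that a reader can judge the hazard. Either fix the order of QST and MRI within the visit, or word the adverse event window in section 6.3 so that it also covers QST done before scan preparation.

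The cost is one sentence and one screening question, plus the two clarifications if adopted. The only data lost are the optional visual-aversion results of the rare participant affected.
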